### **5.3.2 Eliciting Adverse Event Information**

A consistent methodology of non-directive questioning should be adopted for eliciting adverse event information at all patient evaluation timepoints. Examples of non-directive questions include the following:

"How have you felt since your last clinic visit?"

"Have you had any new or changed health problems since you were last here?"

### **5.3.3 Assessment of Severity of Adverse Events**

The adverse event severity grading scale for the NCI CTCAE (v5.0) will be used for assessing adverse event severity. Table 2 will be used for assessing severity for adverse events that are not specifically listed in the NCI CTCAE.

**Table 2 Adverse Event Severity Grading Scale for Events Not Specifically Listed in NCI CTCAE Toxicity Grading Scale**

Grade	Severity
1	Mild; asymptomatic or mild symptoms; clinical or diagnostic observations only; or intervention not indicated
2	Moderate; minimal, local, or non-invasive intervention indicated; or limiting age-appropriate instrumental activities of daily living a
3	Severe or medically significant, but not immediately life-threatening; hospitalization or prolongation of hospitalization indicated; disabling; or limiting self-care activities of daily living b, c
4	Life-threatening consequences or urgent intervention indicated d
5	Death related to adverse event d

NCI CTCAE = National Cancer Institute Common Terminology Criteria for Adverse Events.

Note: Based on the most recent version of NCI CTCAE (v5.0), which can be found at: [http://ctep.cancer.gov/protocolDevelopment/electronic\\_applications/ctc.htm](http://ctep.cancer.gov/protocolDevelopment/electronic_applications/ctc.htm)

- a Instrumental activities of daily living refer to preparing meals, shopping for groceries or clothes, using the telephone, managing money, etc.
- b Examples of self-care activities of daily living include bathing, dressing and undressing, feeding oneself, using the toilet, and taking medications, as performed by patients who are not bedridden.
- c If an event is assessed as a "significant medical event," it must be reported as a serious adverse event (see Section 5.4.2 for reporting instructions), per the definition of serious adverse event in Section 5.2.2.
- d Grade 4 and 5 events must be reported as serious adverse events (see Section 5.4.2 for reporting instructions), per the definition of serious adverse event in Section 5.2.2.

### 5.3.4 Assessment of Causality of Adverse Events

Investigators should use their knowledge of the patient, the circumstances surrounding the event, and an evaluation of any potential alternative causes to determine whether an adverse event is considered to be related to the study drug, indicating "yes" or "no" accordingly. The following guidance should be taken into consideration (see also [Table 3](#)):

- Temporal relationship of event onset to the initiation of study drug
- Course of the event, with special consideration of the effects of dose reduction, discontinuation of study drug, or reintroduction of study drug (as applicable)
- Known association of the event with the study drug or with similar treatments
- Known association of the event with the disease under study
- Presence of risk factors in the patient or use of concomitant medications known to increase the occurrence of the event
- Presence of non-treatment-related factors that are known to be associated with the occurrence of the event

**Table 3 Causal Attribution Guidance**

Is the adverse event suspected to be caused by the study drug on the basis of facts, evidence, science-based rationales, and clinical judgment?	
YES	There is a plausible temporal relationship between the onset of the adverse event and administration of the study drug, and the adverse event cannot be readily explained by the patient's clinical state, intercurrent illness, or concomitant therapies; and/or the adverse event follows a known pattern of response to the study drug; and/or the adverse event abates or resolves upon discontinuation of the study drug or dose reduction and, if applicable, reappears upon re-challenge.
NO	An adverse event will be considered related, unless it fulfills the criteria specified below. Evidence exists that the adverse event has an etiology other than the study drug (e.g., preexisting medical condition, underlying disease, intercurrent illness, or concomitant medication); and/or the adverse event has no plausible temporal relationship to administration of the study drug (e.g., cancer diagnosed 2 days after first dose of study drug).

For patients receiving combination therapy, causality will be assessed individually for each protocol-mandated therapy.

### **5.3.5 Procedures for Recording Adverse Events**

Investigators should use correct medical terminology/concepts when recording adverse events on the Adverse Event eCRF. Avoid colloquialisms and abbreviations.

Only one adverse event term should be recorded in the event field on the Adverse Event eCRF.

#### **5.3.5.1 Diagnosis versus Signs and Symptoms**

A diagnosis (if known) should be recorded on the Adverse Event eCRF rather than individual signs and symptoms (e.g., record only liver failure or hepatitis rather than jaundice, asterixis, and elevated transaminases). However, if a constellation of signs and/or symptoms cannot be medically characterized as a single diagnosis or syndrome at the time of reporting, each individual event should be recorded on the Adverse Event eCRF. If a diagnosis is subsequently established, all previously reported adverse events based on signs and symptoms should be nullified and replaced by one adverse event report based on the single diagnosis, with a starting date that corresponds to the starting date of the first symptom of the eventual diagnosis.

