#### **4.1.1 Inclusion Criteria**

Patients must meet the following criteria for study entry:

- Written informed consent/assent for study participation obtained from patient's parents or legal guardian, with assent as appropriate by the patient, depending on the patient's level of understanding
- Aged 1 to <12 years at randomization (Day 1)
- Parent/guardian willing and able to comply with study requirements, in the investigator's judgment
- Patient able to comply with study requirements, depending on the patient's level of understanding
- Patient with a diagnosis of influenza virus infection confirmed by the presence of all of the following:
  - Fever  $\geq 38^{\circ}\text{C}$  (tympanic temperature) at screening
  - At least one respiratory symptom (either cough or nasal congestion)

- The time interval between the onset of symptoms and screening is  $\leq 48$  hours (the onset of symptoms is defined as the time when body temperature first exceeded 37.5°C if known, or the time when the first symptom was noticed by patient, parent, or caregiver)

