### **5.3.1 Adverse Event Reporting Period**

Investigators will seek information on adverse events at each patient contact. All adverse events, whether reported by the parent/caregiver or patient or noted by study personnel, will be recorded in the patient's medical record and on the Adverse Event eCRF.

After informed consent has been obtained but prior to initiation of study drug, only serious adverse events caused by a protocol-mandated intervention (e.g., invasive procedures such as biopsies, discontinuation of medications) should be reported (see Section 5.4.2 for instructions for reporting serious adverse events).

After initiation of study drug, all adverse events will be reported until 28 days after the last dose of study drug.

Instructions for reporting adverse events that occur after the adverse event reporting period are provided in Section 5.6.

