### **5.3.5.3 Persistent or Recurrent Adverse Events**

A persistent adverse event is one that extends continuously, without resolution, between patient evaluation timepoints. Such events should only be recorded once on the Adverse Event eCRF. The initial severity (intensity or grade) of the event will be recorded at the time the event is first reported. If a persistent adverse event becomes more severe, the most extreme severity should also be recorded on the Adverse Event eCRF. If the event becomes serious, it should be reported to the Sponsor immediately (i.e., no more than 24 hours after learning that the event became serious; see Section 5.4.2 for reporting instructions). The Adverse Event eCRF should be updated by changing the event from "non-serious" to "serious," providing the date that the event became serious, and completing all data fields related to serious adverse events.

A recurrent adverse event is one that resolves between patient evaluation timepoints and subsequently recurs. Each recurrence of an adverse event should be recorded as a separate event on the Adverse Event eCRF.

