#### **All Adverse Events**

Only treatment-emergent AEs will be summarized. Treatment-emergent events are defined as those AEs with observed or imputed onset date on or after the start date of trial treatment. Only where the most extreme intensity is greater than the initial intensity (or if most extreme intensity is not missing and initial intensity is missing) will events with an onset date prior to the start of study treatment be considered treatment-emergent. An AE with a completely missing start date will be assumed to be treatment-emergent unless the AE has a complete non-imputed end date that is prior to study Day 1.

Adverse events will be coded and tabulated by SOC and/or PT. In tabulations, PTs and their associated SOC will be presented in order of descending frequency summed across the treatment arms. Adverse events will also be tabulated by severity and relationship to the study drug as indicated by the investigator. Adverse events leading to withdrawal, AEs leading to death, and AEs leading to a dose modification or interruption will be summarized.

The following will also be summarized by treatment, and listings produced where required:

- Serious AEs
- AEs leading to withdrawal
- AEs leading to death
- AEs leading to a dose modification or interruption
- Non-serious AEs occurring in  $\geq 5\%$  of patients in at least one treatment group
- Non-serious AEs occurring in  $\geq 1\%$  of patients in at least one treatment group

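### A diagnosis made after dosing but dated to a pre-dose symptom can drop out of the primary safety tables unless its recorded grade later rises

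*Protocol*

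**What the plan says.** Four rules act together.

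- **Dating (Protocol 5.3.5.1).** Once a diagnosis is established, "all previously reported adverse events based on signs and symptoms should be nullified and replaced by one adverse event report" for that diagnosis, "with a starting date that corresponds to the starting date of the first symptom of the eventual diagnosis". No limit is set at the first dose.
- **Selection (SAP 4.5.1, All Adverse Events).** The adverse event tables are confined to one class, which is identified by calendar date: "Treatment-emergent events are defined as those AEs with observed or imputed onset date on or after the start date of trial treatment". An event with an earlier date is kept on one condition: "Only where the most extreme intensity is greater than the initial intensity", or where the initial intensity is missing and the most extreme one is not.
- **Initial grade (Protocol 5.3.5.3).** "The initial severity (intensity or grade) of the event will be recorded at the time the event is first reported".
- **Collection before dosing (Protocol 5.3.1).** "After informed consent has been obtained but prior to initiation of study drug, only serious adverse events caused by a protocol-mandated intervention" are to be reported.

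The opening paragraph of SAP 4.5.1 uses a different criterion. It bases the safety analyses on events reported once the first dose has been given, whatever their onset date.

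**The concern.** Protocol 4.1.1 admits children who already have fever plus cough or nasal congestion, with onset up to 48 hours before screening. Those symptoms can also be the first signs of bronchitis, sinusitis or pneumonia. A complication recognised some days after dosing could therefore carry a start date before Day 1. The symptom reports it replaces are nullified, so no other record of the event would remain in the tables.

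The incidence and timing of adverse events are the primary endpoint (SAP 2.2.1), and the sample size rests on the chance of seeing an uncommon event at all. The event types are realistic: Protocol 1.2.2 lists bronchitis and sinusitis among the relatively common adverse events of the adult and adolescent Phase III study.

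**Working it through.** **1. The plan's own figure.** Protocol 6.2 and SAP 2.3 give the probability of at least one case among 80 baloxavir marboxil patients. The formula is 1 − (1 − p)^80. At p = 3% this is 1 − 0.97^80 = 91.3%. For 1% to 5% it gives 55.2%, 80.1%, 91.3%, 96.2% and 98.3%, which matches the published row.

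**2. Following one record through the rules.** Illustrative child: cough starts the day before Day 1, the dose is given on Day 1, worsened cough is reported as an adverse event on Day 3, and bronchitis is diagnosed on Day 4 with a worst grade of 2.

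| Start date entered | Initial grade on the diagnosis record | Worst grade | In the SAP summaries? |
|---|---|---|---|
| Day before Day 1 | 2 (grade when the diagnosis is reported) | 2 | No |
| Day before Day 1 | 1 (carried over from the replaced report) | 2 | Yes, grade rose |
| Day before Day 1 | Missing | 2 | Yes |
| Day 3 | 2 | 2 | Yes |

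If the cough had instead begun on Day 1 but before the dose, the event would still count, because the SAP compares calendar dates. The first row is the gap. The initial grade is fixed at a report made after dosing, so the exception cannot see that the illness grew out of milder symptoms before dosing. The documents do not say whether a replacement record keeps the grade of the report it replaces, so they do not decide between the first and second rows.

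**3. What the onset-date filter can properly remove.** Under Protocol 5.3.1 the only events reportable before study drug are serious ones caused by a protocol-mandated intervention. Almost any other record with an earlier onset date was therefore reported after dosing. The filter has little legitimate work to do.

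**4. Sensitivity of the detection figure.** Let f be the share of cases of one event type that the filter excludes. The documents give no value for f, so the range is an assumption. Detection becomes 1 − (1 − 0.03 × (1 − f))^80.

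| f | Probability of at least one recorded case, true incidence 3%, n = 80 |
|---|---|
| 0% | 91.3% |
| 10% | 88.8% |
| 20% | 85.7% |
| 30% | 81.7% |
| 50% | 70.2% |

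The 90% target needs a recorded incidence of at least 1 − 0.1^(1/80) = 2.84%. It is missed once f exceeds 1 − 0.0284/0.03, about 5.4%. This applies only to diagnoses whose early symptoms resemble influenza, not to adverse events in general.

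**The case against.** The strongest reply is that the dating sentence is narrow. It governs only the case where symptoms were already reported as adverse events and a diagnosis then replaces them. Entry fever and cough are not adverse event reports: conditions present at screening go on the medical history form (Protocol 5.3.5.8), and expected influenza symptoms are not recorded unless they worsen unexpectedly (5.3.5.9). The replaced reports will normally be post-dose, and a sensible investigator will use the earliest of them. A complication diagnosed outright replaces nothing. The entry cough can also be held to belong to influenza and not to the later diagnosis. Protocol 5.3.5.2 further asks for an independent record when a medically significant secondary event arises at a distinct time. The arms are blinded, the analysis is descriptive, and SAP 4.8 keeps all deaths in the safety analyses.

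Most of this stands, and it limits how often the gap will open. It does not close it. The start date is tied to the first symptom of the diagnosis, not to the first adverse event reported, so dating to the entry cough is permitted though not required. Protocol 5.3.5.2 gives no rule for a continuous cough that becomes bronchitis. The two criteria in SAP 4.5.1 still give different answers for the same record.

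**Conclusion.** The gap is real but conditional. An event is lost when three things coincide: the investigator dates the diagnosis to a symptom from a calendar day before treatment, an initial grade is recorded, and the worst grade does not exceed it. The likely result is some under-counting in both arms. How much cannot be derived from the documents.

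A reader might infer more, and four stronger readings are not supported:

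- **That the SAP drops every event with onset before treatment.** It keeps those that worsen, those with a missing initial grade, and those dated to the day of treatment.
- **That a number of lost children can be stated.** This would need rates for such diagnoses, for literal dating and for unchanged grade, none of which the documents give. A child who loses one diagnosis also stays in the any-event count if another event was recorded.
- **That the arms are biased against each other.** The same rule applies to both blinded arms, and no differential loss is shown.
- **That the influenza-complications endpoint loses the same events.** SAP 4.6.1 counts complications after treatment from the adverse event pages, without invoking the treatment-emergent definition.

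The change is still worth making, because the rule bears on the primary endpoint, removes almost nothing that ought to be removed, and costs little to correct.

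**What to change.** **SAP 4.5.1.** Reconcile the two criteria in one sentence: any adverse event first reported after the first dose is treatment-emergent whatever its recorded onset date, and the only events excluded are serious ones caused by a study procedure that occurred before dosing.

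**eCRF completion guidance.** State that influenza symptoms present before dosing do not set the start date of a diagnosis made later. This also protects the timing part of the endpoint, which the SAP sentence alone does not.

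**Cost.** One sentence in each document. The downside is that a few illnesses already present at entry will be counted as treatment-emergent, in both arms alike.

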### **5.3.5.2 Adverse Events That Are Secondary to Other Events**

In general, adverse events that are secondary to other events (e.g., cascade events or clinical sequelae) should be identified by their primary cause, with the exception of severe or serious secondary events. A medically significant secondary adverse event that is separated in time from the initiating event should be recorded as an independent event on the Adverse Event eCRF. For example:

- If vomiting results in mild dehydration with no additional treatment in a healthy adult, only vomiting should be reported on the eCRF.
- If vomiting results in severe dehydration, both events should be reported separately on the eCRF.
- If a severe gastrointestinal hemorrhage leads to renal failure, both events should be reported separately on the eCRF.
- If dizziness leads to a fall and consequent fracture, all three events should be reported separately on the eCRF.
- If neutropenia is accompanied by an infection, both events should be reported separately on the eCRF.

All adverse events should be recorded separately on the Adverse Event eCRF if it is unclear as to whether the events are associated.

### **5.3.5.3 Persistent or Recurrent Adverse Events**

A persistent adverse event is one that extends continuously, without resolution, between patient evaluation timepoints. Such events should only be recorded once on the Adverse Event eCRF. The initial severity (intensity or grade) of the event will be recorded at the time the event is first reported. If a persistent adverse event becomes more severe, the most extreme severity should also be recorded on the Adverse Event eCRF. If the event becomes serious, it should be reported to the Sponsor immediately (i.e., no more than 24 hours after learning that the event became serious; see Section 5.4.2 for reporting instructions). The Adverse Event eCRF should be updated by changing the event from "non-serious" to "serious," providing the date that the event became serious, and completing all data fields related to serious adverse events.

A recurrent adverse event is one that resolves between patient evaluation timepoints and subsequently recurs. Each recurrence of an adverse event should be recorded as a separate event on the Adverse Event eCRF.

### **5.3.5.4 Abnormal Laboratory Values**

Not every laboratory abnormality qualifies as an adverse event. A laboratory test result must be reported as an adverse event if it meets any of the following criteria:

- Is accompanied by clinical symptoms
- Results in a change in study treatment (e.g., dosage modification, treatment interruption, or treatment discontinuation)

- Results in a medical intervention (e.g., potassium supplementation for hypokalemia) or a change in concomitant therapy
- Is clinically significant in the investigator's judgment

It is the investigator's responsibility to review all laboratory findings. Medical and scientific judgment should be exercised in deciding whether an isolated laboratory abnormality should be classified as an adverse event.

If a clinically significant laboratory abnormality is a sign of a disease or syndrome (e.g., ALP and bilirubin 5 × upper limit of normal [ULN] associated with cholestasis), only the diagnosis (i.e., cholestasis) should be recorded on the Adverse Event eCRF.

If a clinically significant laboratory abnormality is not a sign of a disease or syndrome, the abnormality itself should be recorded on the Adverse Event eCRF, along with a descriptor indicating whether the test result is above or below the normal range (e.g., "elevated potassium," as opposed to "abnormal potassium"). If the laboratory abnormality can be characterized by a precise clinical term per standard definitions, the clinical term should be recorded as the adverse event. For example, an elevated serum potassium level of 7.0 mEq/L should be recorded as "hyperkalemia."

Observations of the same clinically significant laboratory abnormality from visit to visit should only be recorded once on the Adverse Event eCRF (see Section 5.3.5.3 for details on recording persistent adverse events).

### **5.3.5.5 Abnormal Vital Sign Values**

Not every vital sign abnormality qualifies as an adverse event. A vital sign result must be reported as an adverse event if it meets any of the following criteria:

- Is accompanied by clinical symptoms
- Results in a change in study treatment (e.g., dosage modification, treatment interruption, or treatment discontinuation)
- Results in a medical intervention or a change in concomitant therapy
- Is clinically significant in the investigator's judgment

It is the investigator's responsibility to review all vital sign findings. Medical and scientific judgment should be exercised in deciding whether an isolated vital sign abnormality should be classified as an adverse event.

If a clinically significant vital sign abnormality is a sign of a disease or syndrome (e.g., high blood pressure), only the diagnosis (i.e., hypertension) should be recorded on the Adverse Event eCRF.

Observations of the same clinically significant vital sign abnormality from visit to visit should only be recorded once on the Adverse Event eCRF (see Section 5.3.5.3 for details on recording persistent adverse events).

### 5.3.5.6 Abnormal Liver Function Tests

The finding of an elevated ALT or AST ( $>3 \times \text{ULN}$ ) in combination with either an elevated total bilirubin ( $>2 \times \text{ULN}$ ) or clinical jaundice in the absence of cholestasis or other causes of hyperbilirubinemia is considered to be an indicator of severe liver injury (as defined by Hy's law). Therefore, investigators must report as an adverse event the occurrence of either of the following:

- Treatment-emergent ALT or AST  $>3 \times \text{ULN}$  in combination with total bilirubin  $>2 \times \text{ULN}$
- Treatment-emergent ALT or AST  $>3 \times \text{ULN}$  in combination with clinical jaundice

The most appropriate diagnosis or (if a diagnosis cannot be established) the abnormal laboratory values should be recorded on the Adverse Event eCRF (see Section 5.3.5.1) and reported to the Sponsor immediately (i.e., no more than 24 hours after learning of the event), either as a serious adverse event or an adverse event of special interest (see Section 5.4.2).

